2. SYRINGE PREPARATION

Only the Principal Investigator or authorized personnel who have been instructed in the proper administration and accountability of the study product will administer the investigational study product. Study product intended for one subject must not be used for another subject. The Investigator must not use material provided for this particular study in another study.

The pharmacy should confirm that the subject has arrived in the clinic prior to preparation of study product.

Approximately 15 to 20 minutes prior to study product preparation remove the vial from the -20°C ($\pm 10^\circ\text{C}$) storage and bring to room temperature. The vial should not be heated or microwaved. **The vial should not be shaken.** AMG0001 is stable at room temperature (25°C) for up to 6 hours.

All preparation should be conducted using controlled and validated aseptic techniques under Biosafety Level 1 (BSL1) conditions, including Bio-Safety Cabinet II (BSC II) or Laminar Flow

Hood (Biosafety Class 1 or International Organization for Standardization (ISO) Class 5). Use of goggles, mask, sterile gloves and lab coat is recommended.

To prepare one administration of the AMG0001:

With a 21 Gauge needle, withdraw 1.7 mL contents of one AMG0001 into a syringe and dilute into a 30 mL sterile vial containing 23.7 mL sterile saline to provide 25.4 mL of a diluted 0.167 mg/mL solution. Slowly invert the 30 mL vial 4 times to provide gentle mixing of study product and diluent. Three (3) mL of the solution should be filled in each of 8 (3 mL) syringes provided by the Sponsor. Each 3 mL syringe of the diluted solution should be used for each of 8 injections during the administration. Syringes must be labeled with the subject number. The overage is provided to ensure that a delivered volume of 3 mL is injected and the residual undelivered volume in the vials and all 8 syringes is accounted for properly. Any residual material should be disposed of in an appropriate manner for biological waste products.

After dilution with sterile saline solution, the diluted study product is physically and chemically stable for 24 hours at 2°C-8°C. If the prepared syringes are refrigerated prior to being administered, they should be left to reach room temperature prior to the start of the injection procedure.

From a microbiological point of view, the product should be used immediately. The product is not intended to be stored after dilution unless this has taken place under controlled and validated aseptic conditions. If not used immediately, in-use storage times and conditions are the responsibility of the user and would normally not be longer than 6 hours up to 25°C or 24 hours at 2°C-8°C.

DO NOT DISCARD USED STUDY PRODUCT VIALS UNTIL AUTHORIZED BY THE STUDY MONITOR.

3. ADMINISTRATION OF INJECTIONS

Based on the injection site locations confirmed by the vascular surgeon, Investigators should mark the initial 8 injection sites with a tattoo pen prior to injecting the study product on Day 0. The procedure will be repeated on injections made on Day 14, Day 28, and Day 42 using a different color tattoo pen to track the injections. The Month 3, Month 9, and Month 12 injection site locations should mirror that of Day 0.

Subsequent injection site locations for the Day 14, Day 28, and Day 42 injection sites will be 1-2 cm initially proximal to the Day 0 injection then 1-2 cm distal and subsequently 1-2 cm lateral, respectively. The Month 3+14 days, Month 3+28 days, Month 3+42 days, Month 9+14 days, Month 9+28 days, Month 9+42 days, and Month 12 + 14 days, Month 12 + 28 days, and Month 12 + 42 days injection site locations should mirror that of Days 14, 28, and 42, respectively.

No more than 3 injections should be made into the anterior or lateral compartments on any dosing visit.

The Investigator should utilize duplex ultra-sound to guide the 8 IM injections.

Investigators must utilize a 21 Gauge, 7cm echotip® needle and the 3mL syringes for the IM injections of study product.

Investigators should trace blood vessels from the proximal portion while maintaining the probe at a right angle with the color Doppler and identify occluded areas. Investigators should select

injection sites as areas of musculature proximal and distal to the occluded sites and areas adjacent to the occlusion where blood flow through the collateral blood vessels.

Investigators should check pulsation with a color Doppler. The blood flow wave should also be examined with a color Doppler in order to exclude venous blood flow if arterial blood flow is poor around the selected injection sites.

Insert the needle while monitoring it under echographic guidance.

Confirm the injection into the muscle under B mode echography by injecting a small amount of the investigational product. If the injection is made into the muscle, the drug is shown to infiltrate in a spherical form. This observation cannot be seen if the injection is made into the fascia or interstitial tissues.

Inject the entire 3mL in the syringe in about 3 seconds. Immediately after completion of injection, lightly press the injection site with the finger in order to prevent reflux.

Do not massage the injection site.

The subject should remain in a supine position while receiving all 8 injections and for 15 minutes post injections.

The time and details of study product administration should be noted in the subject's source documentation and CRF.

Photographs of the injection site locations (with ruler) must be taken at the completion of each dose.

[figure not shown]
4. ADMINISTRATION METHOD

Below are suggested needle approaches for the administration of study product to muscular anatomy supplied by commonly occluded arteries. The popliteal artery is branched into the anterior tibial artery (ATA), posterior tibial artery (PTA), and peroneal artery.

4.1 OCCLUSION OF THE AREA SUPPLIED BY THE ATA

ATA is distributed in a deep layer of compartments consisting of a group of extensor muscles such as the anterior tibial muscle and the long extensor muscle of the great toe. Collateral blood vessels are also distributed in these compartments. Apply the echo probe from the lateral site of the Tibia and make the injection into these extensor muscles. The ATA perforates the interosseous membrane right beneath the knee joint. If occlusion occurs in the area proximal to this perforation site, no efficacy can be expected even if injection is made into the component consisting of extensor muscles. It is recommended that injection not be made in such compartment.

[figure not shown]
4.1 Occlusion of the area supplied by the ATA

4.2 OCCLUSION IN THE AREA SUPPLIED BY THE PTA

The PTA is distributed between the soleus muscle and a deeper compartment. Collateral blood vessels maybe distributed in both compartments. The surface of the proximal portion of the crus (2/3) is covered with the gastrocnemius muscle. In order to inject the drug into the soleus muscle, the gastrocnemius muscle must be perforated with the needle. When a distal portion of the crus is targeted, checking based on ultra-sound guided images and injection are easy since the superficial gastrocnemius muscle is thin and the needling depth is shallow. In contrast, if the target tends to be in the deeper proximal areas and observation is difficult, make approach from just behind the tibia, i.e., from the medial side and stab the needle into the muscle such as the long flexor muscle of the digits.

[figure not shown]
4.2 Occlusion of the area supplied by the PTA

[figure not shown]
[figure not shown]
4.3 STUDY PRODUCT PREPARATION & ADMINISTRATION

[figure not shown]
[figure not shown]
The peroneal artery is distributed into a layer deeper than the long flexor muscle of the digits. Make approach from just behind the fibula, identify the deeper long flexor muscle of the digits using the fibula as a marker, and stab the needle into this muscle.

4.3 Occlusion of the area supplied by the Peroneal Artery

In 4.2 and 4.3 above, attention is required not to stab the needle into the gastrocnemius muscle. Because blood vessels are more branched in the gastrocnemius muscle than in the popliteal region, increases in collateral circuits in the gastrocnemius muscle compartment are not expected to contribute to increases in peripheral blood flow in the lower limbs.

Examples of Injection Site Location Scenarios are Given Below:

APPENDIX B. HEMODYNAMIC PROCEDURES

ABI and TBI Assessment

Explain the procedure, reassure the subject, and ensure that he/she is lying flat and is comfortable, relaxed, and rested with no pressure on the proximal lower limb vessels. Laying the subject supine reduces the hydrostatic pressure inaccuracies. Reliability and ability to reproduce results both over time and between observers was tested and the index was found to vary by 0.06, which is considered acceptable. Measuring the pressure in both arms and using the higher of the two pressures increases the non-invasive accuracy of measurement of central systolic pressure but will not eliminate this potential limitation to the method.

Measure the brachial systolic blood pressure:

1. Place an appropriately sized cuff around the upper arm
2. Locate the brachial pulse and apply ultrasound contact gel
3. Angle the Doppler probe at 45 degrees and move the probe to obtain the best signal
4. Inflate the cuff until the signal is abolished then deflate the cuff slowly and record the pressure at which the signal returns being careful not to move the probe from the line of the artery
5. Repeat the procedure for the other arm
6. Use the highest of the two values to calculate the ABI

Measure the ankle systolic pressure:

1. Place an appropriately sized cuff around the ankle immediately above the malleoli having first protected any ulcer that may be present
2. Examine the foot, locating the dorsalis pedis pulse and apply contact
3. Continue as for the brachial pressure, recording this pressure in the same way
4. Repeat this for the posterior tibial artery
5. Use the highest reading obtained to calculate the ABI for that leg

Measure the toe systolic pressure:

1. Place an appropriately sized cuff around the hallux (1st toe) having first protected any ulcer that may be present. If the 1st toe is unavailable you may use other toes if appropriate, this should be documented in the source documents.
2. Examine the toe with the Doppler or PPG (photoplethysmograph), locating the pulse on the dorsal aspect and apply contact.

Note: The same method (Doppler or PPG) must be used on the subject for all assessments through study completion.

3. Continue as for the ankle pressure, recording this pressure in the same way
4. Repeat this for the plantar toe artery
5. Use the highest reading obtained to calculate the TBI for that leg

Problems and errors may arise if:

1. The cuff is repeatedly inflated or inflated for long periods. This can cause the ankle pressure to fall.
2. The cuff is not placed at the ankle.
3. The pulse is irregular or the cuff is deflated too rapidly.
4. The true systolic pressure may be missed and inappropriately high reading will be obtained, if the vessels are calcified (associated with diabetes), the legs are large, fatty or edematous, the cuff size is too small, or the legs are dependent.
5. Central systolic pressure may influence the 'normal' range for the ABI.

For subjects with ankle and toe pressures in the affected limb that are not reliable due to non-compressible arteries or unattainable due to ulcers on ankle or great toe, there must be documentation of diagnosis of severe Rutherford category 4 or Rutherford category 5 and angiographic evidence of total occlusion of the superficial femoral, popliteal or at least one of the infra-popliteal arteries.

APPENDIX C. RUTHERFORD CLASSIFICATION

Rutherford Categories

Category	Clinical Description
Asymptomatic	
1.	Mild claudication
2.	Moderate claudication
3.	Severe claudication
4.	Ischemic rest pain
5.	Minor tissue loss
6.	Major tissue loss

APPENDIX D. WOUND CARE GUIDELINES

The purpose of these guidelines is to ensure that wound care during the study is consistent across all study subjects.

General Guidelines for Wound Care

All ulcers in both the treatment and control groups will receive wound care as summarized below for the duration of the study.

Debridement

Sharp or surgical debridement will be performed as deemed necessary by a wound care specialist (e.g. doctors/nurses at wound care clinics, orthopedic physicians, podiatrist, etc). If it is deemed necessary for any study subject, this procedure should always precede any photographic or ulcer tracing assessment. There are many debriding agents, but there is no consensus about the best agent. The method of debridement that is chosen will depend on the status of the wound, the resources of the healthcare provider and the overall condition of the subject. When chosen, this procedure should remove crusts as well as necrotic, devitalized tissue by surgical, enzymatic, mechanical, biological or autolytic debridement.

Treatment

Maintenance of a clean, moist ulcer environment is essential. Ideally, this should include daily dressing changes. Select a dressing that is cost-effective, appropriate to ulcer etiology, the setting and the provider. Dressing changes once daily or less often should be chosen where possible. Ulcer care products that can be utilized for study subjects include: saline, hydrogel, negative pressure dressings and topical antibiotics. Wound care products such as Regranex® (rhPDGF), Apligraft®, Dermagraft®, Oasis®, as well as any other skin equivalents or topical growth factors are **excluded** for use during this trial. Hyperbaric oxygen (HBO) treatment is also excluded.

Continuing education of the subject in regards to risk factor reduction should be addressed as frequently as necessary. This includes cigarette smoking cessation, control of any diabetes, elevated homocysteine levels, hyperlipidemia and hypertension. Additionally, where possible, exercise to increase arterial blood flow has been demonstrated to be helpful in long-term maintenance and arterial ulcer prevention.

Pressure relief by off-loading can also be pursued based on recommendations from the wound care specialist. Acceptable offloading methods include crutches, walker, wheelchair, custom shoes, depth shoes, shoe modifications, custom shoe inserts, custom relief orthotic walker, diabetic boots, forefront and heel relief shoes, and total contact casts.

Ref: Chronic Wound Care Guidelines, The Wound Healing Society, [name]. [contact]. www.woundheal.org

APPENDIX E. THE VISUAL ANALOG SCALE (VAS) PROCEDURES - MEASURING REST PAIN

Pain Intensity rating using VAS

The visual analog scale (VAS) is a 10-cm line, oriented horizontally, with the left end of the line (the 0 mark) indicating “no pain” and the right end representing “pain as bad as it can be”.

1. The subject is asked to mark a place on the line corresponding to the average pain intensity experienced in the last seven days.
2. The distance along the scale is then converted into a numeric reading by measuring the distance of the subjects mark in centimeters from the beginning of the scale (the 0 mark).

THE MEASUREMENT IS RECORDED IN CENTIMETERS FROM 00.0 TO 10.0 ONTO SOURCE DOCUMENTATION AND THE CRF.

The measurements will not be divulged to the subject. Additionally, the pain scale or VAS score from previous visits will not be shown to the subject.

APPENDIX F. POST 18-MONTH FOLLOW-UP QUESTIONNAIRE

Instructions: You may wish to seek your doctor's help in answering these questions.

Please consult your physician if you need help with any of these medical conditions.

"Diseased Leg" in this questionnaire refers to the diseased leg that received the injections of study product.

Diseased Leg (circle): RIGHT LEFT

Since your last visit or follow-up with this study, have you experienced any of the conditions mentioned below?

1. Any new or recurring cancer(s)? YES NO
 - a. If yes, what type of cancer and when was it diagnosed? _____
 - b. What cancer treatment did you receive? None Surgery Chemotherapy Radiation Other (describe) _____
2. Any new problems with your eyesight? YES NO
 - a. Did you see the eye doctor? YES NO
 - b. If yes, what was the diagnosis and how were you treated? _____
3. Have you had any significant, unexplained bleeding from anywhere? YES NO
 - a. If yes, give details of location, diagnosis and treatment. _____
4. Have you been diagnosed with an autoimmune disorder (e.g., Rheumatoid arthritis, Lupus, Asthma)? YES NO
 - a. If yes, please give details: _____
 - b. How were you treated? _____
5. Have you been diagnosed with a blood disorder (e.g., anemia, platelet disorder, low white cell count)? YES NO
If yes, please answer the following questions:
 - a. When did it happen? _____
 - b. What was the diagnosis? _____
 - c. What treatment did you receive? _____
 - d. What was the outcome? _____

6. Have you been diagnosed with a new nerve disorder or has there been a flare-up of an existing nerve disorder? YES NO

If yes, please answer the following questions:

- a. What was the condition? _____
- b. When was it diagnosed? _____
- c. How was it treated? _____

7. Have you had any other unexpected or significant new illness? YES NO

If yes, please describe the illness: _____

8. Have you been hospitalized? YES NO,

If yes, please describe _____

9. Have you suffered from a stroke (transient or long-lasting)? YES NO

If yes, please describe _____

10. Have you suffered from a myocardial infarction (heart attack)? YES NO

If yes, please describe _____

11. Have you had any revascularization procedure performed on your diseased leg?

YES NO

If yes, please describe and specify which leg: _____

12. How are your symptoms relating to ulcers, gangrene and/or rest pain on your diseased leg? Improved Same Worse

13. Have you had an amputation above the ankle of either leg? YES NO

a. If yes, please describe and specify which leg: _____

b. Please indicate date of amputation: _____

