4.7. Peripheral Vascular Intervention History (or Update)

During Screening

At Screening, the Investigator will perform a detailed assessment of all past peripheral vascular interventions (surgical bypass, an endovascular intervention or major/minor amputations). If the subject has never undergone a peripheral vascular intervention then the lack of these events will be documented as well. Information may include: date(s) of intervention, type(s) of intervention (e.g., PTA, surgical bypass, amputation, etc.), intervention site (e.g., iliac, femoro-popliteal, infrapopliteal, etc.), intervention side (right or left leg and index or non-index leg) conduit used (e.g., saphenous vein, polytetrafluoroethylene [PTFE], human umbilical vein [HUV], Dacron, etc.), and patency of most recent intervention prior to study start (including a description of the results from the most recent vascular imaging if available). Information concerning both major (defined as at or above the ankle) and minor (below the ankle) amputation should be collected. Specific information for each peripheral vascular procedure will be obtained and recorded on the

subjects' source documentation and CRF to allow independent review of the subjects' CLI status and suitability for entry into the study.

During Treatment and Follow up Period

During the study, detailed information must be documented in the subjects' source documentation and CRF on the subject's CLI status of the index leg including any treatment received for worsening CLI of the index leg, plan for major or minor amputations of the index leg, plan for revascularization procedures of the index leg, etc. Detailed information on the subjects' CLI status must be documented prior to planning a surgical revascularization or major amputation of the index leg. Data relating to the reasons for performing a surgical revascularization or major amputation of the index leg will be reviewed.

In no way will intervention that is deemed necessary be withheld for any subject.

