9. EVALUATIONS AND STATISTICAL METHODS

9.1. Evaluations

The following evaluations relating to tolerability, safety and clinical benefit will be made:

1. Adverse events (AEs) suspected to be related to injections of HGF plasmid
2. Discontinuations related to adverse effects from the injections of HGF plasmid
3. All AEs up to Month 3, Month 6, Month 12, and Month 18
4. Serious adverse events (SAEs) up to Month 3, Month 6, Month 12, and Month 18
5. Number of deaths and cause over the 18 month period up to Month 3, Month 6, Month 12, and Month 18
6. Number of subjects in whom the largest ulcer healed completely or gets smaller (photo confirmation) at 6, 12 and 18 months (cumulative)
7. Number of subjects in whom rest pain (based on the 100 mm VAS scale) reduces by 20 mm or more or was completely relieved at 6, 12 and 18 months (cumulative)
8. Change in VascuQol Questionnaire (QOL) score compared to the baseline at 6, 12 and 18 months
9. Number of subjects revascularized (bypass or endovascular intervention) up to Month 3, Month 6, Month 12, and Month 18
10. Number of subjects with minor and number of subjects with major amputations (at or above the ankle) up to Month 3, Month 6, Month 12, and Month 18

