10. SAFETY FOLLOW-UP PROGRAM

Since this study uses a DNA plasmid for gene transfer, the Sponsor (AnGes, Inc.) is complying with regulatory guidance to conduct long-term safety follow-up to collect safety information on all participants who receive the study product. The long-term safety follow-up data will be collected every 6 months for an additional 18 months following the Month 18 Visit.

Adverse Events should be documented and followed from the start of the first dose of study product (Day 0), until the final outcome is known or until the end of the study safety follow-up period. AEs (including SAEs) that have not resolved by the end of the study follow-up period should be recorded in the CRF as "ongoing". If it is not possible to obtain a final outcome for a SAE, the reason that a final outcome could not be obtained must be documented (e.g., completion of follow up, subject has moved and cannot be contacted, etc.). Serious Adverse Events should be reported within 24 hours of site awareness.

Deaths, major amputations, revascularizations by surgical bypass, stroke, and myocardial infarction will be source verified. An appropriate request/permission for this safety follow-up program will be included in the informed consent.

The data collected during the follow-up period will consist of surgical revascularization, lower limb amputation, cancers, eyesight changes, bleeding/blood disorders, autoimmune diseases, neurological disorders, hospitalizations, unexpected or significant illnesses including stroke, myocardial infarction, and death. In the event of death, information regarding the above data (as best as possible) and date and cause of death will be requested from a spouse or nearest relative. The questionnaire is found in Appendix F.

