Additional visits for HGF protein and HGF plasmid DNA sample collection will be conducted on Day 4 and Month 12+4 days for all subjects, and additionally HGF plasmid DNA assay sample collection on Month 9+4 days for the first 5 enrolled subjects (i.e. subjects who receive any study treatment). Long-term safety follow-up data using a questionnaire will be obtained every 6 months following the Month 18 visit at the Month 24, Month 30 and Month 36 time points. Subject data collection during the Long Term Follow-up (LTFU) period (post-Month 18 visit) will be limited to Serious Adverse Events (SAEs) and the visit questionnaire data intended to assess the occurrence of any potential gene-therapy related delayed AEs. The total duration of the study will be up to 37 months.

Subjects will not be eligible to receive the subsequent doses of the study product if major amputation of the index leg has occurred, where the index leg is defined at the leg with the greater severity of CLI disease (also referred to as the treated leg or affected leg).

All eligible subjects will receive AMG0001 intramuscularly in the muscles of the index leg based on the location of disease.

Schedule of Study Procedures

PROCEDURES	Study Day (visit window*) - Visit # (V)	Screening Period	Dosing Visits: First Cycle												Dosing Visits: Second Cycle												Post-Month 18 Long Term Follow-up															
			Days -30 to -1				Day 0 - V1				Day 14 ($\pm 2d$) - V2				Day 28 ($\pm 2d$) - V3				Month 3 ($\pm 7d$) - V5				Month 3+14 Days ($\pm 2d$) - V6				Month 3+28 Days ($\pm 2d$) - V7				Month 3+42 Days ($\pm 2d$) - V8				Follow-Up		Follow-Up		Follow-Up		Follow-Up	
*d=days																																										
Subject Consent & Medical History	X																																									
Vital Signs, Weight & Height ⁽³⁾	X	X	X	X	X	X	X	X	X	X	X	X	X	X	X	X	X	X	X	X	X	X	X	X	X	X	X	X	X	X	X											
12-Lead ECG	X																																									
Physical Examination ⁽⁶⁾	X ⁽¹⁰⁾	X ⁽¹⁰⁾	X ⁽¹¹⁾	X ⁽¹¹⁾	X ⁽¹¹⁾	X ⁽¹⁰⁾	X ⁽¹¹⁾	X ⁽¹¹⁾	X ⁽¹¹⁾	X ⁽¹⁰⁾	X ⁽¹⁰⁾	X ⁽¹⁰⁾	X ⁽¹⁰⁾	X ⁽¹⁰⁾	X ⁽¹⁰⁾	X ⁽¹⁰⁾	X ⁽¹⁰⁾	X ⁽¹⁰⁾	X ⁽¹⁰⁾	X ⁽¹⁰⁾	X ⁽¹⁰⁾	X ⁽¹⁰⁾	X ⁽¹⁰⁾	X ⁽¹⁰⁾	X ⁽¹⁰⁾	X ⁽¹⁰⁾	X ⁽¹⁰⁾	X ⁽¹⁰⁾	X ⁽¹⁰⁾	X ⁽¹⁰⁾	X ⁽¹⁰⁾	X ⁽¹⁰⁾										
Peripheral Vascular Intervention Update ⁽⁶⁾	X ⁽¹⁾	X ⁽¹⁾																																								
CLI Assessment ⁽⁷⁾	X ⁽¹⁾	X ⁽¹⁾																																								
Hemodynamic Measurements ^(6,7)	X ⁽¹⁾	X ⁽¹⁾																																								

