A summary table including counts and percentages and a listing will be provided for these parameters for the following time periods: up to Month 6, 0 to Month 12, and 0 to Month 18.

As a supplemental analysis, time to major amputation or death will be performed, and the Kaplan-Meier (KM) estimates with 2-sided 95% confidence interval using Greenwood's formula will be computed up to the end of the study and plotted. If a subject undergoes major amputation followed by death, it will be counted as an event. If a subject does not experience major amputation or death, the subject will be censored at the date of last contact as recorded on the CRFs.

- **Shift from baseline in Rutherford classification**

Shift from baseline in Rutherford classification will be summarized by study visit.

- **Quality of life (QoL)**

Quality of life (QoL) measurements will be assessed using the disease-specific vascular Quality-of-Life questionnaire (VascuQol). The VascuQol contains 5 domains (pain, symptom, activities, social, and emotional functioning), and responses are scored from 0 (lowest QOL imputed after death) to 7 (best QOL, maximum health). Responses are averaged for composite overall and domain-specific scores, giving equal weight to each question and domain. Subjects' data after revascularization or major amputation will be included in the analysis. However, after death, subjects will be scored as 0. For the effect of treatment on individual domains, pain, symptoms, and activity will be considered the most important of the 5 domains.

Summary statistics will be provided for baseline and change from baseline by visit for each score including total and domain scores. At each visit, only subjects who have a non-missing value at both baseline and the specific visit will be summarized, and two-sided one-sample t-tests for the change-from-baseline will be performed for each visit and LOCF.

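### Question 13 of the post-Month-18 questionnaire leaves out amputation at the ankle, so a major amputation could be missed or misclassified in the supplemental Kaplan-Meier analysis

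*Protocol*

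**What the plan says.** Several places in the protocol define major amputation in the same way. Section 4.7 states: "Information concerning both major (defined as at or above the ankle) and minor (below the ankle) amputation should be collected". Section 9.1 lists the "number of subjects with major amputations (at or above the ankle) up to Month 3, Month 6, Month 12, and Month 18". The Introduction and exclusion criterion 2 use the same boundary.

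After Month 18, Appendix F question 13 asks: "Have you had an amputation above the ankle of either leg". Its sub-items (description, leg, date) follow from a yes. No other item on the form names amputation at any level.

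Protocol section 10 sets a wider scope for the same period: "The data collected during the follow-up period will consist of surgical revascularization, lower limb amputation, cancers", with no restriction on level. SAP section 2.2 says that data collection after Month 18 "will be limited to Serious Adverse Events (SAEs) and the visit questionnaire data".

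SAP section 2.5.5 states: "As a supplemental analysis, time to major amputation or death will be performed". The estimates "will be computed up to the end of the study and plotted". For a subject with neither event, "the subject will be censored at the date of last contact as recorded on the CRFs". The SAP does not define major amputation itself.

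**The concern.** The Kaplan-Meier event is ascertained in two ways within one curve. Up to Month 18, clinic visits apply the boundary at or above the ankle. From Month 18 to Month 36, which is 18 of the 36 months, the routine source is a form whose only amputation question has a narrower boundary. A subject whose foot was removed at the ankle could answer no to question 13 without being wrong. If nothing else brought the event to light, that subject would be censored at last contact as free of major amputation. Any error of this kind runs in one direction, towards better amputation-free survival.

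There is also a mismatch of scope. Section 10 promises lower limb amputation in general, and the form has no question about amputation below the ankle.

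Confirming that study activities are feasible ahead of the phase 3 study is a primary objective, so a wording fault in a data collection form is the kind of thing this pilot should bring out.

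**Working it through.** The plan states no amputation rate, event count or expected survival, so there is no figure of its own to reproduce. The check is a comparison of texts, followed by an illustration of scale.

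**1. Does the form's boundary match the endpoint's?**

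| Level of amputation | Protocol 4.7 and 9.1 | Protocol section 10 scope | Appendix F question 13 |
|---|---|---|---|
| Above the ankle | Major | Collected | Asked |
| At the ankle | Major | Collected | Not asked |
| Below the ankle | Minor | Collected | Not asked |

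The second row matters for the survival endpoint. The third row conflicts with section 10 only.

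**2. Does the analysis reach the period the form covers?** The curve runs to the end of the study. SAP section 2.2 places questionnaires at Months 24, 30 and 36 and counts them within a total duration of up to 37 months. On that reading, yes.

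**3. Is serious adverse event reporting a second source?** It depends on the leg.
- *Index leg:* Protocol section 8.1.2 sends interventions for worsening CLI, including major amputation, to the CLI section of the CRF rather than to SAE reporting. The exceptions are events that are unexpected for the natural history or closely tied in time to the product. This route is therefore largely closed.
- *Non-index leg:* Protocol section 8.1.1 has minor and major amputations recorded as AEs or SAEs. This route is open for events that meet the serious criteria.

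The gap therefore falls mainly on the treated leg.

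**4. Scale if one event goes unrecorded.** Inputs: n = 8 to 10 subjects (Protocol section 3). Assumptions, not from the documents: one at-ankle amputation after Month 18, not captured by any route, with no later death on study.

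With r subjects at risk and current estimate S, recording the event would take the estimate to S × (1 − 1/r). Missing it therefore leaves the estimate too high by S/r.

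*No earlier censoring.* Here S = r/n, so S/r = 1/n however many events came before:
- n = 10: 1/10 = 10 percentage points
- n = 8: 1/8 = 12.5 percentage points

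*With earlier censoring.* Suppose two earlier events, so that S = (n − 2)/n, followed by censoring that leaves 4 or 5 at risk:

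| n | S | r | S/r |
|---|---|---|---|
| 8 | 0.75 | 4 | 0.188 |
| 8 | 0.75 | 5 | 0.150 |
| 10 | 0.80 | 4 | 0.200 |
| 10 | 0.80 | 5 | 0.160 |

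That is about 15 to 20 points. With no at-ankle amputation after Month 18, the error is zero.

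**The case against.** A reader might infer that at-ankle amputations after Month 18 are missed, and that survival is therefore biased upward. The documents do not support that, because question 13 is not the only way such an event could surface:

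- Question 8 asks about any hospitalization, with a description, and question 7 about any other significant new illness.
- Site staff obtain the answers by telephone and may ask for more information or medical records (Protocol section 10).
- Section 10 tells the site to obtain dates and treatments for amputation of the index limb, whatever the level, and says major amputations will be source verified.
- The form invites subjects to seek their doctor's help, and a lay subject may well not separate at from above the ankle.

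These points stand as reasons to say could be missed rather than are missed. They do not close the gap. Question 8 does not ask about amputation, its level, its side or its date. Section 10 ties the request for further information to the event types noted in the questionnaire, and an at-ankle amputation is not one that question 13 names.

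It is also fair to say that little rests on the result. The analysis is supplemental, the study is descriptive and not powered for inference, and the planned counts of major amputation stop at Month 18 without using this form. That stands, and it sets the priority.

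**Conclusion.** The wording mismatch is real and its consequence is conditional. An amputation at the ankle after Month 18, chiefly of the index leg, could go unrecorded or be misclassified, and the subject could be censored as event-free in the supplemental Kaplan-Meier analysis. The size is 10 to 12.5 percentage points per unrecorded event without earlier censoring, and more with it. This is an illustration, not an estimate of bias: the expected effect cannot be computed from the documents. A subject who later died on study would still count as an event, only later.

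The conclusion assumes that the end of the study means the end of long-term follow-up, and that the protocol's definition of major amputation governs the SAP endpoint.

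A reader might also infer that the absent question on minor amputation affects the results. It does not affect any planned analysis: minor amputations are counted only to Month 18 and are not part of the Kaplan-Meier endpoint. It remains an inconsistency with section 10. Overall this is a low-priority alignment of wording, worth making because the possible error runs in one direction and is easily removed.

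**What to change.** Reword question 13 along these lines: *Have you had any amputation of either leg or foot? If yes, specify the leg, the date and the level (at or above the ankle, or below the ankle).* This brings the form into line with the endpoint definition and with section 10 in one step, and lets the level be classified from the answer.

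For questionnaires already completed, query whether any amputation has occurred since Month 18, with its level and date, and check the hospitalization answers for amputations reported there.

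The cost is one line in an appendix, the ethics notification or review that the change needs, and a short round of queries in a study of 8 to 10 subjects.
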